**1.4.2. Pharmacokinetic Parameters**

Descriptive summaries will be provided on the pharmacokinetic endpoints, details will be documented in a separate Pharmacokinetic Analysis Plan (PKAP).

**1.4.3. Safety Parameters**

The safety endpoints are:

PPD

- Safety and tolerability assessed by the frequency and severity of AEs, AEs of special interest, vital signs, and laboratory evaluations from Baseline after approximately 52 weeks on a therapeutic regimen of setmelanotide compared to placebo
- Change in ambulatory BP and heart rate (HR) from Baseline after approximately 52 weeks on a therapeutic regimen of setmelanotide compared to placebo (in patients  $\geq 12$  years)

## 2. ANALYSIS POPULATIONS

### 2.1. Population Definitions

The following analysis populations will be used in the statistical analyses:

- **Screening Analysis Set:** is defined as all patients who signed the informed consent form.
- **Safety Analysis Set (SA):** is defined as all patients who received at least 1 dose of study treatment (placebo or setmelanotide). Analyses performed on the safety set will be based on patients according to the treatment received.
- **Full Analysis Set (FAS):** is defined as all randomized patients. Analyses performed on the FAS will be based on treatment as randomized.
- **Modified Intention-to-Treat Analysis Set (mITT):** is defined as all randomized patients who are exposed to at least 1 dose of study treatment. Analyses performed on the mITT will be based on treatment as randomized.
- **Per-Protocol Set (PP):** is defined as all patients in the mITT without any major protocol violations that warrant exclusion as determined by Sponsor in process described in [Section 2.2](#).

The mITT is the primary population for the analysis of efficacy data. The PP will be used for sensitivity analyses of primary and key secondary efficacy endpoints. The SA is the primary population for the analysis of safety endpoints.

### 2.2. Protocol Violations

At the discretion of the Sponsor, major protocol violations, as determined by a review of the data prior to unblinding of the study results and the conduct of statistical analyses, may result in the removal of a patient's data from the PP Set. The Sponsor or designee will be responsible for producing the final protocol violation file (formatted as a Microsoft Excel file), in collaboration with the data monitoring group (or designee) as applicable; this file will include a description of each protocol violation and clearly identify whether or not this violation warrants exclusion from the PP Set. This file will be finalized prior to database lock and unblinding.

All protocol violations will be presented in a data listing.

### 3. GENERAL STATISTICAL METHODS

#### 3.1. Sample Size Justification

The sample size is mainly driven by the primary efficacy hypothesis with the safety database taken into consideration. With the planned sample size of ~120 patients (~80 patients in setmelanotide group vs ~40 patients in placebo group), the trial provides ~99.5% power to detect a treatment difference (treatment - placebo) of -10% in percent change of BMI from baseline after approximately 52 weeks on a therapeutic regimen of setmelanotide at 2-sided alpha of 0.05, assuming a common standard deviation of 10% (estimated from trial RM-493-030), a dropout rate of 20%, and 2:1 randomization.

It is planned to enroll ~12 patients from Japan within the ~120 patients. Using the Method 1 described in PMDA guidance, simulation studies (nsim = 100000 runs) confirmed that the sample size of 12 Japanese patients will provide 80.1% probability that  $D_{\text{Japan}}/D_{\text{all}} > 0.5$  (D: Difference between study drug and placebo for the primary endpoint).

#### 3.2. General Methods

All data listings that contain an evaluation date will contain a relative study day (Rel Day). Pre-treatment and on-treatment study days are numbered relative to the date of randomization which is designated as Day 1. The preceding day is Day -1, the day before that is Day -2, etc. The last day of study medication is designated with an "L" (e.g., Day 14L). Post-treatment study days are numbered relative to the last dose and are designated as Day 1P, Day 2P, etc.

All output will be incorporated into Microsoft Word or Excel files, or Adobe Acrobat PDF files, sorted and labeled according to the International Conference on Harmonisation (ICH) recommendations, and formatted to the appropriate page size(s).

Tabulations will be produced for appropriate demographic, baseline, efficacy, pharmacokinetic, and safety parameters. For categorical variables, summary tabulations of the number and percentage of patients within each category (with a category for missing data) of the parameter will be presented. For continuous variables, the number of patients, mean, median, standard deviation (SD), minimum, and maximum values will be presented.

Unless stated otherwise, all relevant statistical tests will be conducted at the 2-sided, 0.05 level of significance.

#### 3.3. Computing Environment

All statistical analyses will be performed using SAS statistical software Version 9.4 or higher, unless otherwise noted. Medical history and AEs will be coded using the Medical Dictionary for Regulatory Activities (MedDRA) Version 25.1 or later. Prior and concomitant medications will be coded using the World Health Organization (WHO) Drug Dictionary Version September 1, 2022 or later.

### 3.4. Baseline Definitions

For all analyses, baseline will be defined as the last available measurement prior to randomization for patients randomized into either the setmelanotide or placebo group.

### 3.5. Methods of Pooling Data

Pooling of data is not applicable to this study.

### 3.6. Adjustments for Covariates

For efficacy analyses, including the primary analysis, where an analysis of covariance (ANCOVA) model, with an unequal variance to account for possible unequal residual variances, will be utilized and multiple age groups and subpopulation (Japanese vs. non-Japanese) are considered, adjustments will be made for the relevant age groups and subpopulation (Japanese vs. non-Japanese) for that given analysis. For example, the primary analysis on BMI for all patients in mITT would be adjusted for age groups of  $\geq 18$  years old,  $\geq 12$  and  $< 18$  years old, and  $< 12$  years old and subpopulation (Japanese vs. non-Japanese), whereas key secondary endpoint of mean change in weekly average of daily most hunger score in patients  $\geq 12$  will be adjusted for age groups of  $\geq 18$  years old and  $\geq 12$  and  $< 18$  years old) and subpopulation (Japanese vs. non-Japanese).

For ANCOVA models run on change as opposed to percent change, such as key secondary endpoint of change in most hunger score, adjustments will be made for baseline values.

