### 7.4. Analysis of the Primary Efficacy Endpoint

The primary objective of this trial is to evaluate the mean percent change in BMI in response to setmelanotide administered SC daily in patients with HO compared to placebo at the end of placebo-controlled trial. To evaluate the primary objective, the primary efficacy endpoint of the trial is the mean percent change in BMI from Baseline after approximately 52 weeks on a therapeutic regimen of setmelanotide.

The statistical hypothesis for the primary efficacy endpoint is:

$$H_0: \mu_t - \mu_p \geq 0 \quad \text{vs} \quad H_1: \mu_t - \mu_p < 0$$

where  $\mu_t$  is the mean percent change in BMI from baseline after approximately 52 weeks on a therapeutic regimen in setmelanotide group, and  $\mu_p$  is the mean percent change in BMI from baseline after approximately 52 weeks on a therapeutic regimen in placebo group.

An analysis of covariance (ANCOVA) model, with an unequal variance to account for possible unequal residual variances, will be used for the primary analysis on the primary endpoint, adjusted with a stratification factor of age groups ( $\geq 18$  years old,  $\geq 12$  and  $< 18$  years old,  $< 12$  years old) and subpopulations (Japanese and non-Japanese). The consistency of efficacy on the primary endpoint in the overall population and the Japanese population will be evaluated. A primary efficacy analysis cohort is defined as the first 120 patients dosed. The primary efficacy analysis will be based on all patients in any region who have completed the trial and any patients who discontinued after receiving their first dose. To ensure the integrity of the study at the site level, investigators and patients will remain blinded after the unblinding of the sponsor for the primary analysis. For patients already enrolled who are still progressing (in any region), missing values will be imputed using multiple imputation. The interaction of treatment effect and subpopulations will be explored and assessed in the statistical model. Descriptive summaries/analysis and graphical displays by subpopulations will be assessed and presented. The statistical hypothesis will be tested at a 2-sided 0.05 significance level. A 2-sided 95% confidence interval (CI) will be calculated and presented. The success criterion for the primary

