
### 4.3.2. Primary Efficacy Analysis

The primary efficacy endpoint of this study is the mean percent change from baseline in BMI after 52 weeks of treatment with the therapeutic regimen of either setmelanotide or placebo.

The statistical hypothesis for the primary efficacy endpoint is:

$$H_0: \mu_t - \mu_p \geq 0 \text{ vs } H_1: \mu_t - \mu_p < 0$$

where  $\mu_t$  is the mean percent change in BMI from baseline after approximately 52 weeks on a therapeutic regimen in setmelanotide group, and  $\mu_p$  is the mean percent change in BMI from baseline after approximately 52 weeks in placebo group.

The primary endpoint will be conducted on the mITT utilizing BMI values resultant from the multiple imputation process as outlined in [Section 3.10.2](#). The difference between setmelanotide and placebo after 52 weeks on therapeutic dose will be estimated using an ANCOVA model with unequal variance to account for possible unequal residual variances. The model will be adjusted with stratification factors of age group ( $\geq 18$  years old,  $\geq 12$  and  $< 18$  years old, and  $< 12$  years old) and subpopulation (Japanese and non-Japanese) as appropriate. This difference will be estimated for each of the 100 imputed datasets. The outcomes from the 100 imputed datasets will be combined using Rubin's Rule ([Little and Rubin, 2002](#)) through SAS PROC MIANALYZE to provide an overall estimate of least squares (LS) mean difference with corresponding 95% confidence intervals (CI) and p-value. The success criterion for the primary hypothesis requires the rejection of the null hypothesis at the 2-sided 0.05 significance level.

While formal hypothesis testing will be considered based on pivotal patients, the primary analysis will also be conducted for all patients.

The primary analysis will be repeated for Japanese patients to explore consistency of effect for the PMDA. Consistency will be determined as an observed treatment effect in Japanese patients of at least 50% of the observed, overall treatment effect (seen in all patients), in alignment with PMDA Method 1. All patients are the basis for comparison as this is the set of patients that consists of all 12 Japanese patients.

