#### **4.3.6.5. Body Weight Percent Change from Baseline in Patients $\geq 18$ Years of Age**

Mean percent change in weight from baseline after approximately 52 weeks in pivotal and all patients  $\geq 18$  years in the mITT will be analyzed.

The between-group comparison on the mean percent change from baseline will be conducted with an ANCOVA model, assuming unequal variance to account for possible unequal residual variances. The ANCOVA model will adjust for the stratification factor of subpopulations (Japanese and non-Japanese), as appropriate.

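### The primary model of percent change in BMI omits baseline BMI; the planned test stays valid, but possible precision and protection against chance imbalance within strata are given up

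*SAP*

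**What the plan says.** The general rule is in SAP 3.6. It begins "For ANCOVA models run on change as opposed to percent change, such as key secondary endpoint of change in most hunger score" and provides for baseline adjustment in those models. Models of percent change fall outside it.

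The sections for the individual endpoints follow the rule:

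- **Primary endpoint, percent change in BMI.** SAP 4.3.2: "The model will be adjusted with stratification factors of age group", together with Japanese/non-Japanese. Protocol 7.4 has the same two factors ("adjusted with a stratification factor of age groups", plus subpopulation), and the synopsis agrees. Baseline BMI is not listed.
- **Percent change in adult weight.** SAP 4.3.6.5: "The ANCOVA model will adjust for the stratification factor of subpopulations". Baseline weight is not listed.
- **Models of change.** Hunger (4.3.5.3), hyperphagia symptoms (4.3.6.2), BMI Z-score and percentile (4.3.6.6), IWQOL (4.3.6.9), waist circumference (4.3.6.10) and cardiometabolic parameters (4.3.6.11) all include the baseline value.

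The tipping-point, per-protocol, as-observed and LOCF analyses (SAP 4.3.3 and 4.3.4) specify no baseline term either. The readable text gives no reason for treating percent change differently.

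**The concern.** Dividing by baseline rescales the outcome. It makes percent change unrelated to baseline only if response is proportional to baseline, and the documents do not show that. If heavier patients lose a larger or smaller share of their BMI, two things follow from leaving baseline out: variance that could be explained stays in the error term, and a chance difference in baseline BMI between the arms moves the estimate in proportion to the slope.

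Age group is a randomisation stratum and a model term, so much of the contrast between children and adults is already handled. What remains is the spread within strata. It may be wide: adults qualify at a BMI of 30 kg/m² with no stated upper limit, and the youngest stratum covers ages 4 to 11. Only about 40 patients are planned on placebo.

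**Working it through.** **Inputs.** From SAP 3.1: 80 versus 40 patients, 20% dropout (so 64 versus 32), two-sided alpha 0.05, a difference of -10 points and SD 10 ("assuming a common standard deviation of 10% (estimated from trial RM-493-030"). The SD is taken here as the within-stratum SD before baseline adjustment. The within-stratum correlation r between baseline BMI and percent change is not in the documents; 0 to 0.4 is assumed, and includes 0.

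**The plan's own figure.** SE = 10 × √(1/64 + 1/32) = 2.165. Power = Φ(10/2.165 − 1.96) = Φ(2.66) = 99.6%; the noncentral t version gives 99.55%. This reproduces the SAP statement that "the trial provides ~99.5% power to detect a treatment difference (treatment - placebo) of -10% in percent change of BMI".

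**With baseline in the model, same slope in both arms.** Residual SD = 10 × √(1 − r²). The equivalent number of extra patients is N × [1/(1 − r²) − 1]. The -5 column is an assumed smaller effect.

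| r | Variance falls | SE (64/32) | 95% half-width, 1.96 × SE | Power at -10 | Power at -5 | Patients at N = 120 | At 96 |
|---|---|---|---|---|---|---|---|
| 0 | 0% | 2.165 | 4.24 | 99.6% | 63.7% | 0 | 0 |
| 0.2 | 4% | 2.121 | 4.16 | 99.7% | 65.4% | 5 | 4 |
| 0.3 | 9% | 2.065 | 4.05 | 99.8% | 67.8% | 12 | 9 |
| 0.4 | 16% | 1.984 | 3.89 | 99.9% | 71.2% | 23 | 18 |

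**With baseline predictive only on setmelanotide.** Under 2:1 allocation the common slope is about 2/3 of the active-arm slope. The residual variance becomes 100 × (1 − 8r²/9) on active and 100 × (1 + 4r²/9) on placebo. The variance of the difference is then 100 × [(1 − 8r²/9)/80 + (1 + 4r²/9)/40]. The r² terms are −8r²/9 and +8r²/9 over 80, and they cancel, so there is no large-sample gain. A simulation at 80/40 agrees: variance rose by about 1% for r = 0.3 or 0.4 on active and 0 on placebo, and fell by 8% for r = 0.3 in both arms.

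**Chance imbalance at 80/40.** The SE of the baseline difference is √(1/80 + 1/40) = 0.194 within-stratum SD. P(|Z| > 0.3/0.194) = 12%, so about one trial in eight would show an imbalance of at least 0.3 SD. At r = 0.3 an imbalance of 0.3 SD moves the unadjusted difference by 0.3 × 10 × 0.3 = 0.9 points, in either direction. The SE at 80/40 is 1.94, so this is a little under half of one SE.

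**Conditional error rate.** A simulation (20,000 runs, 64/32, equal variances, no strata) looked only at trials whose baseline imbalance exceeded 1.5 SE. At r = 0.3 the type I error was about 7.5% unadjusted and 4.7% adjusted. At r = 0 it was about 5.5% and 5.0%.

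**The case against.** The strongest reply is that nothing here is an error. Randomisation makes the unadjusted comparison valid, and its standard error already allows for chance imbalance. That stands. A reader might infer from the 7.5% figure that the primary test is biased or that its type I error is inflated. The documents do not support this: the figure applies only to trials that happen to be imbalanced.

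A reader might also infer that the trial is underpowered or needs more patients. It does not: at the design effect the planned power is already about 99.5%, and the patient equivalents only express precision.

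Three further points stand. The correlations are assumed, and at 0 nothing is gained. Only the correlation within age strata counts, so the span from young children to adults overstates the problem. The gain also needs a similar slope in both arms.

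Using baseline weight in the imputation (SAP 3.10.2) but not in the analysis model may look inconsistent, but it is not a defect: an imputation model may hold more variables than the analysis model. Finally, SAP Section 5 (changes to planned analyses) is blacked out, so whether it gives a reason for the percent-change rule cannot be known.

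None of this argues for leaving the covariate out. The high power rests on an assumed effect and SD, the interval is reported whatever the p-value, and an observed imbalance would invite an adjusted analysis that nobody had prespecified.

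**Conclusion.** The point holds as one of efficiency and robustness. The two percent-change models leave out a covariate that is already collected, and the readable text gives no reason. The planned primary test is valid, and its success at the design effect is unlikely to turn on this.

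The possible gain is a variance reduction between 0% and 16% for within-stratum correlations of 0 to 0.4 that are similar in both arms. At a correlation of 0.3 the 95% half-width narrows from about 4.24 to 4.05 points. There is little or no gain, and possibly a loss of about 1%, if baseline predicts response only on setmelanotide. The benefit would matter more if the true effect were smaller than planned or if the arms happened to differ at baseline. The reading of the text is certain; the size of the benefit is not, because the documents give no correlation.

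**What to change.** Before the sponsor is unblinded:

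- Add continuous baseline BMI to the primary model in SAP 4.3.2 and Protocol 7.4, and to the analyses that repeat it (tipping-point, per-protocol, as-observed, LOCF and the all-patients version).
- Add baseline weight to the model in SAP 4.3.6.5.
- In SAP 3.6, remove the distinction between change and percent change, so that baseline is a covariate in both.

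The cost is one degree of freedom per model and no new data. Protocol Section 7 requires major changes to the primary analysis to appear in a protocol amendment as well, so the two documents should be changed together. The sample size does not change. If the sponsor prefers to keep the primary model as it is, a prespecified baseline-adjusted sensitivity analysis would supply the adjusted estimate, but the primary interval would not benefit.

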### 3.7. Multiple Comparisons/Multiplicity

No multiplicity adjustments are required for the primary analysis as this study has only 1 primary endpoint. This controls the overall alpha at 0.05, 2-sided.

There are 3 key secondary efficacy endpoints planned in the trial. Based on the rarity of this disease, and the small number of patients to be enrolled in this trial, the ability to use extremely rigorous statistical approaches to address multiplicity for these key secondary endpoints is limited. Therefore, for publication, nominal-p-values will be used to interpret each endpoint separately in this small trial. The Sponsor acknowledges that this approach may increase the probability of potential Type 1 error for the set of 3 key secondary efficacy endpoints being analyzed. Therefore, if the primary endpoint is successfully met, then the Sponsor intends to apply a step-down (i.e. sequential testing/fixed sequence testing) on the 3 key secondary endpoints to control the overall Type 1 error, if needed for this purpose.

The following order will be used for sequential testing purposes:

- The proportion of patients with  $\geq 5\%$  reduction in BMI in adult patients ( $\geq 18$  years of age), or BMI Z-score reduction of  $\geq 0.2$  points in pediatric patients from Baseline after approximately 52 weeks on a therapeutic regimen of setmelanotide treatment compared to placebo.
- The proportion of all patients with  $\geq 5\%$  reduction in BMI from Baseline after approximately 52 weeks on a therapeutic regimen of setmelanotide compared to placebo.

- Mean change in the weekly average of the daily most hunger score in patients  $\geq 12$  years old from Baseline after approximately 52 weeks on a therapeutic regimen of setmelanotide treatment compared to placebo.

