## **7.5. Analysis of the Secondary Efficacy Endpoints**

### **7.5.1. Key Secondary Efficacy Endpoints**

Due to the rarity of the disease indication and small sample size, formal multiplicity adjustment procedures will not be enforced. However, to assist the comprehensive assessment and interpretation of the efficacy of setmelanotide, appropriate statistical testing will be performed on the key secondary efficacy endpoints according to the following hierarchical order to control the overall type I error rate. The p-values and the corresponding CIs will be provided.

- The proportion of patients with  $\geq 5\%$  reduction in BMI in adult patients ( $\geq 18$  years of age), or BMI Z-score reduction of  $\geq 0.2$  points in pediatric patients ( $< 18$  years of age) from Baseline after approximately 52 weeks on a therapeutic regimen of setmelanotide compared to placebo.

The between-group comparison on the proportion of patients with  $\geq 5\%$  reduction in BMI in adult patients ( $\geq 18$  years of age), or BMI Z-score reduction of  $\geq 0.2$  in pediatric patients ( $< 18$  years of age) from Baseline after approximately 52 weeks on a therapeutic regimen will be conducted with a Cochran–Mantel–Haenszel (CMH) test with adjustment of stratification factors of age group and subpopulation (Japanese

and non-Japanese). The associated corresponding 2-sided 95% CI will be presented. The analysis will be based on the mITT.

- The proportion of all patients with  $\geq 5\%$  reduction in BMI from baseline after approximately 52 weeks on a therapeutic regimen of setmelanotide compared to placebo.

The between-group comparison on the proportion of all patients with  $\geq 5\%$  reduction in BMI from baseline after approximately 52 weeks on a therapeutic regimen will be conducted Cochran–Mantel–Haenszel (CMH) test with adjustment of stratification factors of age group and subpopulation (Japanese and non-Japanese) at a 2-sided 0.05 significance level. The associated corresponding 2-sided 95% CI will be presented. The analysis will be based on the mITT.

- Mean change in the weekly average of the daily most hunger score in patients  $\geq 12$  years old from Baseline after approximately 52 weeks on a therapeutic regimen of setmelanotide compared to placebo.

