### **4.3.5. Key Secondary Efficacy Analyses**

Statistical testing will be performed on the key secondary endpoints according to the pre-specified hierarchical order as outlined in [Section 3.7](#). Formal inference of efficacy tests will be based on the pivotal patients and stop once a result showing no statistical significance in favor of the study drug at the 2-sided alpha level of 0.05 is achieved.

The key secondary endpoints will rely upon the imputed values utilized for the primary efficacy endpoint (BMI/BMI Z-Score) or rely upon newly imputed values following same methodology as the primary efficacy endpoint (weekly average in daily hunger) as outlined in [Section 3.10.3](#).

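### The plan gives two rules for when a key secondary endpoint counts as positive: a fixed stop rule for formal inference, and separate nominal p-values for publication with a step-down only if needed

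*SAP*

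**What the plan says.** Four places bear on the point.

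- **SAP 4.3.5.** Key secondary testing follows the pre-specified order. Formal inference uses the pivotal patients and is to "stop once a result showing no statistical significance in favor of the study drug at the 2-sided alpha level of 0.05 is achieved". No condition is attached.
- **SAP 3.7.** "There are 3 key secondary efficacy endpoints planned in the trial". After citing the rarity of the disease and the small sample, the section says that "for publication, nominal-p-values will be used to interpret each endpoint separately in this small trial". It then concedes the consequence for the set of three: "The Sponsor acknowledges that this approach may increase the probability of potential Type 1 error". Finally, if the primary endpoint is met, the Sponsor intends to apply a step-down "on the 3 key secondary endpoints to control the overall Type 1 error, if needed for this purpose". The order is listed. Who judges the need, when, and by what criterion is not.
- **Protocol 7.8.** It repeats the nominal-for-publication sentence and the intention to apply a step-down after a successful primary endpoint. It does not contain the clause about need.
- **Protocol 7.5.1.** It says that "formal multiplicity adjustment procedures will not be enforced". The next sentence says that testing will nevertheless follow the hierarchical order so as to control the overall type I error rate.

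The order is the same throughout: the combined adult BMI / paediatric Z-score responder endpoint, then 5% BMI responders in all patients, then change in daily most hunger in patients aged 12 years or older.

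**The concern.** The two SAP sections do not give the same answer for an endpoint below a failed step. Suppose either responder endpoint misses 0.05 and hunger has p < 0.05. Under SAP 4.3.5 the sequence has stopped and hunger supports no formal claim. Under the publication rule in SAP 3.7 and Protocol 7.8, hunger is interpreted on its own p-value.

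Because the need for the step-down has no criterion, nothing in SAP 3.7 prevents that judgement from being made after the Sponsor has been unblinded for the primary analysis (SAP 1.3.3). The study report and the publication could then reach different conclusions on the same endpoint from the same data.

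The stated reason also gives only weak support. Small sample size argues against methods that divide alpha. A fixed sequence divides none: each step is tested at the full two-sided 0.05.

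**Working it through.** **Inputs from the documents.** Three key secondary endpoints, each tested at two-sided 0.05 (SAP 3.2, 3.7, 4.3.5); success means significance in favour of drug (SAP 4.3.5). Neither document gives a family-wise error for the three endpoints or correlations between them, so the correlations below are assumptions.

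**The plan's own figures.** For the primary endpoint alone, "This controls the overall alpha at 0.05, 2-sided". That is correct for a single test. The stated power of about 99.5% also reproduces. With 20% dropout, 80 and 40 patients become 64 and 32. The standard error is 10 × √(1/64 + 1/32) = 2.165, so the difference of 10 is 4.62 standard errors, and Φ(4.62 − 1.96) = 99.6% (99.55% with the noncentral t on 94 df). Under the design assumptions the primary gate will almost always open, so the rule for the key secondary endpoints is likely to matter.

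**Fixed sequence.** A false claim requires rejection of the first true null in the order. That test is run at 0.05, so the family-wise error is at most 5% two-sided, or 2.5% in favour of drug. In simulation with all three nulls true it was 4.97% to 5.03% two-sided.

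**Three separate nominal tests, all three nulls true.**

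- Independent, two-sided: 1 − 0.95³ = 14.3%. Upper bound under any dependence: 3 × 0.05 = 15.0%.
- Independent, in favour of drug: 1 − 0.975³ = 7.3%. Upper bound: 3 × 0.025 = 7.5%.

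Independence is not realistic, because the first two endpoints are the same criterion in adults. The table shows simulated rates for three correlated normal test statistics (2 million draws per setting).

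| Correlation of the two responder endpoints | Correlation of each with hunger | Any error, two-sided | Any error in favour of drug |
|---|---|---|---|
| 0 | 0 | 14.3% | 7.3% |
| 0.5 | 0.3 | 13.3% | 6.7% |
| 0.7 | 0.3 | 12.6% | 6.3% |
| 0.9 | 0.5 | 10.8% | 5.4% |

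The first and last rows are the extremes over all settings run (0 to 0.9 between the responder endpoints, 0 to 0.5 with hunger).

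**Fewer true nulls.** With two true nulls and independence the nominal approach gives 1 − 0.95² = 9.75% two-sided, or 1 − 0.975² = 4.9% in favour of drug. With one true null there is no inflation.

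**The case against.** The strongest reply is that the rules differ in scope, so they do not conflict. SAP 4.3.5 is unconditional and governs formal inference. SAP 3.12.1 ties formal testing and the study's conclusion to the same pivotal cohort. The nominal rule is confined to publication, and the Sponsor openly acknowledges its effect. Much of this stands, and it rules out several stronger readings.

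- A reader might infer that the plan fails to control the type I error over the key secondary endpoints. It does not fail if SAP 4.3.5 is followed as written.
- A reader might infer that both documents make the step-down conditional on need. Only SAP 3.7 does; Protocol 7.8 states an intention without that clause.
- A reader might take Protocol 7.5.1 as abandoning control. Its next sentence keeps the hierarchy for exactly that purpose, and one fair reading is that no alpha is split and an order is used instead.
- A reader might quote 14.3% as the error rate. It needs all three nulls true, independence, and errors counted in both directions.
- Neither document says that a publication will call an endpoint below the stop significant. The text permits such a presentation; it does not announce it.

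The reply leaves three things unresolved. SAP 4.3.5 takes its order from SAP 3.7, the dedicated multiplicity section, and that section makes the procedure conditional. The Protocol 7.5.1 statement on enforcement is not limited to publications. And separation by scope still allows the report and the publication to disagree.

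**Conclusion.** The concern holds as an inconsistency in the decision rule. Formal inference under SAP 4.3.5 is controlled at two-sided 0.05, and the primary test is unaffected. SAP 3.7, with partial support from Protocol 7.5.1 and 7.8, provides a second rule under which an endpoint below a failed step could be presented as positive, and leaves use of the step-down to an undefined judgement.

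If all three key secondary nulls are true, interpreting the endpoints separately carries a family-wise error of about 10.8% to 14.3% two-sided, or 5.4% to 7.3% in favour of drug, against at most 5% and 2.5% under the fixed sequence. In each setting run that is at least about twice the fixed-sequence level. The range rests on assumed correlations and approximately normal test statistics, and the inflation is smaller when fewer nulls are true.

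**What to change.** Before the Sponsor is unblinded, align both documents with SAP 4.3.5:

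1. In SAP 3.7 and Protocol 7.8, replace *intends to apply* with *will apply*.
2. In SAP 3.7, delete the closing condition about need in "to control the overall Type 1 error, if needed for this purpose".
3. In Protocol 7.5.1, delete the statement that "formal multiplicity adjustment procedures will not be enforced", and keep the sentence that sets out the hierarchy.
4. State the SAP 4.3.5 stop rule in both documents as the sole basis for any confirmatory claim: the primary endpoint first, then the three key secondary endpoints in the listed order.
5. In SAP 3.7 and Protocol 7.8, replace the nominal-p sentence with a statement that p-values after the stopping point are descriptive in the study report and in publications, and are shown with confidence intervals.

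This changes wording only. No alpha is split, and no patients or data are added. It is not free of power cost: hunger, which is last and tested only in patients aged 12 years or older, can be claimed only if every earlier step succeeds. SAP 4.3.5 already accepts that cost. Its size cannot be computed, because the documents give no power for the key secondary endpoints.
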